398 (sections 4.5.3 and 6.3.1). This additional Preschool Randot retest without prism and without
399 overminus should occur after all initial stereoacuity testing has been completed (ie. after the

400 Titmus Fly at near) and before the control of exodeviation assessment. This testing without prism
401 and overminus is for an exploratory analysis and is not considered in the determining whether

402 the patient meets surgical failure criteria.

403

404 Rationale:

405 Although patients wearing prism will have stereoacuity measured with prism, is of interest to
406 know whether a patient classified as a success would still be classified as a success if the patient
407 had been measured without prism. Because ‘success’ only applies to the 3-year visit (whereas
408 failure can be called at any visit from 6 months onward), we propose to measure stereoacuity

409 both with prism and without prism at the 3-year visit only. The with-prism measurement will
410 count toward the primary outcome, and the without-prism measurement will be used in an
411 exploratory analysis which would avoid calling a patient a success at 3-years on the basis of a
412 better stereo that is enhanced by prism. The same logic should apply to patients wearing
413 deliberate overminus—ie. stereoacuity should be measured with the overminus throughout the
414 study but that it should be repeated without the overminus at the 3-year exam with this latter test
415 used in the exploratory analysis.

416
417
418
419

420 **This amendment also provides for the following minor protocol clarifications:**

- 421 • Clarified guidelines for prescribing the spherical component of refractive correction (sections
422 2.2.1 and 5.3.2)
- 423 • Specified test distances for stereoacuity testing and for ocular alignment testing (sections 2.5,
424 4.3, 4.4, 4.5).
- 425 • Clarified refractive error eligibility criteria that treatment with prism or overminus lenses
426 must be discontinued at least one week prior to enrollment (section 2.2.1).
- 427 • Clarified eligibility criteria that visual acuity in the worse eye must be ‘0.3 logMAR or
428 better,’ to eliminate confusion about whether ‘at least 0.3 logMAR’ meant at least 0.3
429 logMAR numerically (meaning worse acuity) or qualitatively (meaning better acuity)
430 (sections 1.4 and 2.2.1).
- 431 • Clarified that hangback, hemi-hangback, and adjustable techniques will not be allowed for

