- 1220 *Table 3*) from the enrollment measurement, or to nil, confirmed by a retest

1221
 1222 **Table 3: Preschool Randot Stereotest**

Baseline Stereoacuity, in arcsec	Level needed at follow up visit to meet surgical failure criteria, in arcsec
40''	200'' or worse
60''	400'' or worse
100''	400'' or worse
200''	800'' or worse
400''	Nil

1223
 1224 *Note that both the initial testing and the retest must be performed by a masked examiner
 1225 (*section 4.5.2*). If a patient appears to have met one or more of the above surgical failure criteria
 1226 but the retest(s) do not confirm that at least one criterion is met, the patient is not considered to
 1227 be a surgical failure.
 1228

1229 Patients will also be considered a surgical failure if they undergo a second surgery or treatment
 1230 with botulinum toxin at any time during the study.
 1231

1232 All patients will continue to return for all protocol-specified follow-up exams regardless of
 1233 whether surgical failure criteria are met.
 1234

1235 **4.5.2 Masked Examiner Testing**

1236 Stereoacuity and ocular alignment testing at the visit must be performed by a masked examiner.
 1237

1238 If retesting is needed, retesting should be performed at least 10 minutes after the initial ocular
 1239 alignment testing.

- 1240
- First, if the surgical failure criterion related to a drop in Preschool Randot stereoacuity at near appears to be met (*section 4.5.1*); the masked examiner will retest Preschool Randot stereoacuity at near.
 - Second, if either of the surgical failure criteria related to presence of a tropia appear to be met (*section 4.5.1*), the masked examiner will retest cover/uncover testing and SPCT at distance and near (if tropia is of sufficient duration to measure).
- 1241
- 1242
- 1243
- 1244
- 1245
- 1246

1247 Because this examiner must be masked to the patient's treatment group, the masked examiner
1248 must be someone other than the investigator/surgeon.

1249

1250 **4.5.3 Patients Wearing Prism and/or Deliberate Overminus at 3-Years**

1251 In addition to the assessments listed in section 4.5, *at the 3-year masked exam only*, patients who
1252 are currently prescribed prism and/or deliberate overminus will have Preschool Randot
1253 Stereoacuity at near repeated in current refractive correction but *without* prism or overminus.
1254 This additional Preschool Randot retest without prism and without overminus should occur after

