6.1.1 Classification of Outcome

At the 3-year visit, each patient's condition will be classified as either surgical failure, success, or indeterminate as follows:

Failure = ANY of the following criteria are met at a visit 6 months or later:

1. Exotropia at distance OR near at any time during the exam (i.e., can be constant or intermittent; determined by a cover/uncover test) with a magnitude of at least 10 PD by SPCT, confirmed by a retest
2. Constant esotropia at distance OR near (determined by at least 3 cover/uncover tests—one must be before any dissociation) with a magnitude of at least 6 PD by SPCT, confirmed by a retest
3. Decrease in Preschool Randot near stereoacuity at least 2 octaves (at least 0.6 log arcsec) (*see Table 3*) from the enrollment measurement, or to nil, confirmed by a retest
4. Reoperation or treatment with botulinum toxin

Success = ALL of the following criteria are met at the 3-year visit:

1. Exodeviation less than 10 PD (tropia or phoria) by PACT at distance and near and reduction of more than 10 PD from largest of distance and near angles at enrollment
2. Esotropia less than 6 PD at distance and near by SPCT
3. No decrease in Preschool Randot stereoacuity of 2 or more octaves from the enrollment stereoacuity and no drop to nil
4. No reoperation or treatment with botulinum toxin
5. No non-surgical treatment for IXT during the study

Indeterminate = ALL of the following criteria are met at the 3-year visit:

1. Patient meets one or more of the following:

- 1439
- Exophoria ≥ 10 PD by PACT at distance or near
 - Exodeviation less than 10PD by PACT at distance and near but no reduction of more than 10 PD from largest of distance and near angles at enrollment
 - Intermittent esotropia or esophoria ≥ 6 PD at distance and/or near
- 1443 2. No decrease in Preschool Randot stereoacuity of 2 or more octaves from the enrollment stereoacuity or a drop to nil
- 1444
- 1445 3. No reoperation or treatment with botulinum toxin
- 1446

1447 **6.2 Secondary Data Analysis**

1448 All secondary analyses will be conducted on the primary cohort and stratified by IXT type.

1449

1450 **6.2.1 Subgroup Analyses**

1451 A secondary analysis will assess whether the treatment group difference in the proportion of patients with surgical failure by 3 years varies in subgroups based on baseline factors.

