1486 years—is at the discretion of an unmasked investigator and therefore could be related to
1487 treatment group. To assist in assessing for potential bias, the extent to which treatment group is
1488 related to the decision to reoperate will be evaluated.
1489

1490 **6.2.3 Success Proportion at 3 Year Timepoint**

1491 The estimated proportion of patients who meet criteria for ‘success’ at the 3-year outcome exam
1492 (section 6.1.1) will be calculated and compared between treatment groups using a Fisher’s exact
1493 test. A 95% confidence interval on the difference of proportions between the two groups also
1494 will be calculated.
1495

1496 The potential for bias in this treatment group comparison is recognized. Once a patient has met
1497 the clinical criteria for surgical failure criteria at an interim follow up visit, the decision to
1498 reoperate—and thus prevent the patient from being classified as a success for the 3 year
1499 analysis—is at the discretion of an unmasked investigator and therefore could be related to
1500 treatment group. To assist in assessing for potential bias, the extent to which treatment group is
1501 related to the decision to reoperate will be evaluated.
1502

1503 **6.2.4 Analysis of Secondary Outcomes**

1504 Additional secondary analyses will be performed to assess whether treatment group differences
1505 exist for secondary outcomes: near stereoacuity, distance stereoacuity, monofixation status as
1506 determined using Titmus stereoacuity data, monofixation status determined as using Preschool
1507 Randot stereoacuity data, development of amblyopia, and quality of life.
1508

1509 **6.3 Exploratory Analyses**

1510 **6.3.1 Exploratory Analyses in Primary Cohort**

1511 Exploratory analyses will be stratified by IXT type and conducted in the primary cohort (i.e.
1512 patients whose largest angle by PACT at enrollment is between 15 and 40 PD inclusive).
1513

1514 As exploratory analyses, the primary analysis comparing failure proportions by 3 years (section
1515 6.1), the comparison of failure proportions at 3 years (6.2.2) the comparison of success
1516 proportions at 3 years (6.2.3) will be repeated using the same outcome classification of surgical
1517 failure, success, or indeterminate as described section 6.1.1., with the following exception:

- 1518 • At the 3-year visit, for patients who are currently prescribed prism and/or deliberate

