1519 overminus: the Preschool Randot at near score to be used for the outcome classification will
1520 be the one tested *without* wearing prism or overminus. If this measurement shows a decrease
1521 of at least 2 octaves (at least 0.6 log arcsec) from the enrollment measurement, or to nil, to
1522 avoid adding to testing burden and to the complexity of visits, a confirmatory retest *is not*
1523 needed to be considered a surgical failure for this analysis.

~~1524~~

1526 **6.3.2 Exploratory Analyses in Patients with Baseline Angle > 40 to 50 PD**

1527 Additional exploratory analyses will be stratified by IXT type and conducted in a secondary
1528 cohort of patients whose largest angle by PACT at enrollment is > 40 to 50 PD.
1529

1530 The proportion of patients with surgical failure by 3 years will be calculated and will be
1531 compared between treatment groups using the same method as for the primary analysis.
1532

1532

1533 **6.4 Safety Analyses**

1534 Postoperative complications will be tabulated according to treatment group.

1535

1536 **6.5 Additional Tabulations and Analyses**

1537 The following will be tabulated according to treatment group:

- 1538 1. Baseline demographic and clinical characteristics
- 1539 2. Baseline data for study completers vs. non-completers
- 1540 3. Protocol deviations

1541

1542 A flow chart will be constructed that accounts for all subjects. Visit completion rates will be
1543 tabulated according to treatment group for each visit. The percentage of subjects with visits
1544 completed in window, out of window, and missed for each visit will be tabulated.

1545

1546 **6.6 Interim Analysis**

1547 There are no plans to formally assess surgical failure at a timepoint earlier than 3 years because it
1548 is the long-term outcome that is of clinical interest and because the treatment groups are
1549 expected to differ in the timing of surgical failure and in the criteria met for surgical failure.

1550 Patients receiving unilateral lateral rectus recession with medial rectus resection (R&R) are
1551 expected to fail earlier, due primarily to consecutive esotropia (i.e., overcorrection) which cannot
1552 be managed with prism, whereas patients receiving bilateral lateral rectus recessions (BLRrec)
1553 are expected to have better short-term motor outcomes but fail later, due primarily to recurrence
1554 of the intermittent exotropia over the long term. A treatment group comparison of failure

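### The without-prism failure reruns in Protocol 6.3.1 change the test condition and drop the confirmatory retest together, so they cannot separate the two effects

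*Protocol*

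**What the plan says.** Three rules bear on this point.

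- **Who is rescored, and how (Protocol 6.3.1).** The exception applies "At the 3-year visit, for patients who are currently prescribed prism and/or deliberate" overminus. Their near Preschool Randot score without prism or overminus replaces the score obtained with it. If that score shows the 2-octave drop, or nil, a retest is not "needed to be considered a surgical failure for this analysis". The stated reason is to "avoid adding to testing burden and to the complexity of visits, a confirmatory retest" would bring.
- **The rule for everyone else.** Failure item 3 in Protocol 6.1.1 requires a drop "from the enrollment measurement, or to nil, confirmed by a retest". The note to Protocol 4.5.1 covers a child who seems to meet a criterion, "but the retest(s) do not confirm that at least one criterion is met, the patient is not considered to" be a failure. Section 1.5 of the March 2017 SAP also counts a child with an incomplete retest as not having failed.
- **Purpose.** Protocol Change #9 of the April 2010 amendment wants to "know whether a patient classified as a success would still be classified as a success if the patient" had been tested without prism, and extends the same logic to overminus.

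Protocol 6.3.1 labels the analysis exploratory. Protocol 4.5.3 keeps the extra test out of the primary outcome. Neither SAP lists the rerun.

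**The concern.** The natural way to read the rerun is to set its failure proportion beside the primary one and attribute the difference to prism or overminus. For the affected children, two things have changed between those figures: the optical condition of the test and the number of tests needed to fail. A child whose stereoacuity is the same with and without prism can be a non-failure in the primary analysis and a failure in the rerun, simply because one poor score now suffices.

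The comparison baseline adds to this. Under Protocol 2.5, a child scoring worse than 40 arcsec at enrollment is retested and the better result is used for eligibility. The March 2017 SAP (Objective #2, stereoacuity step) takes the best enrollment value as the reference. A single later test set against the better of two is tilted towards showing a drop.

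What is at stake is the interpretation of an exploratory result. A reader could conclude that prism or overminus was masking stereoacuity loss when part of the change comes from the scoring rule. If the arms differ in how many such children they have, the treatment difference in the rerun would shift as well.

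**Working it through.** **Decomposition.** For a child on prism or overminus at 3 years with no other failure, let W1 be a qualifying drop on the first test with prism or overminus, W2 the same on the confirming retest, and N a qualifying drop on the test without them.

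- Primary analysis: failure if W1 and W2.
- Rerun: failure if N.
- Difference: P(N) − P(W1 and W2) = [P(N) − P(W1)] + [P(W1) − P(W1 and W2)].

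The first bracket is the effect of interest. The second is the effect of dropping confirmation; it equals P(W1 and not W2) and cannot be negative. The rerun reports only the sum.

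**Size of the second bracket.** Section 6.3.1 gives no figure to reproduce, so the inputs below are assumptions, shown as ranges:

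- f, the chance that a child with stable stereoacuity shows a qualifying drop on one test: 5–20%
- ρ, the correlation between test and retest results: 0–0.6 (both are compared with the same enrollment value, so some positive correlation is likely)
- q, the share of an arm on prism or overminus at 3 years: 5–20%

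P(W1 and W2) = f² + ρf(1 − f), so the excess per affected child is f(1 − f)(1 − ρ).

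| f | Excess at ρ = 0.6 | Excess at ρ = 0 |
|---|---|---|
| 5% | 1.9 points | 4.75 points |
| 10% | 3.6 points | 9.0 points |
| 20% | 6.4 points | 16.0 points |

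At f = 10%, for example, one test gives 10% false failures. Confirmation lowers this to 1.0% at ρ = 0 and to 6.4% at ρ = 0.6.

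**Effect on an arm (multiply by q).**

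- Smallest: 0.05 × 0.05 × 0.95 × 0.4 = 0.00095, about 0.1 point. With 96 children in R/R this is 0.09 of a child.
- Largest: 0.20 × 0.20 × 0.80 × 1 = 0.032, or 3.2 points. With 101 children in BLR this is 3.2 children.

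**Failure by 3 years.** Children who have already failed cannot fail again. The K-M inputs in the March 2017 SAP code are 0.4594 (BLR) and 0.3731 (R/R), leaving 0.5406 and 0.6269 not failed. If affected children had failed at their arm's overall rate (an assumption), the range becomes about 0.095 × 0.5406 = 0.05 point to 3.2 × 0.6269 = 2.0 points.

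**Effect on the treatment difference, before that adjustment.** If 5% of one arm and 20% of the other were affected, the shift is (0.20 − 0.05) × f(1 − f)(1 − ρ). This runs from 0.15 × 0.0475 × 0.4 = 0.3 point to 0.15 × 0.16 = 2.4 points, with no prism effect at all. The sign depends on which arm has more such children.

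**Scale.** From the same SAP inputs, the difference is 0.4594 − 0.3731 = 8.6 points. Its standard error is √(0.0518² + 0.0520²) = 0.0734, or 7.3 points, and the 95% CI is −5.8 to 23.0 points.

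**The case against.** The strongest reply is that this is a disclosed trade-off. The protocol states the waiver and its reason, calls the analysis exploratory and keeps it away from the primary outcome. A single-test rule can also be defended as a deliberately strict sensitivity check, and neither SAP lists the rerun. All of this stands and limits the point to interpretation. It does not make the two effects separable: giving the reason for the waiver does not tell a reader that the contrast with the primary analysis is confounded.

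Two stronger readings are tempting but unsupported.

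- **That the success rerun is also faulty.** Success item 5 requires "No non-surgical treatment for IXT during the study", so a reader might infer that swapping the stereoacuity score can hardly change who is a success. But if item 5 already bars children treated for exodeviation, no success among them can rest on prism or overminus, and an unchanged proportion would be correct reassurance. The 2018 SAP (section 1.5 and Objective #4) bars only treatment for a recurrent or residual exodeviation and allows treatment for esodeviation, so on that reading children on prism for esodeviation can still change class. Success item 3 mentions no retest. Waiving item 5 would ask a different question from the one in Change #9.
- **That the bias runs against R&R.** Protocol 6.6 expects R&R failures to come early, from esotropia that prism cannot manage, and BLRrec failures to come late, from recurrence. Protocol 4.4.1 asks for an attempt to reduce or stop prism at each later visit. Which arm has more children on prism or overminus at 3 years is not stated, and overminus for recurrence could be commoner after BLRrec.

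**Conclusion.** The point holds for the failure reruns in 6.3.1, both by and at 3 years. For children prescribed prism and/or deliberate overminus at 3 years, a change from the confirmed result cannot be divided between removing prism or overminus and removing confirmation. The existence and sign of the second component follow from the rules alone. Its size does not: the 0.1 to 3.2 points per arm rest entirely on assumed values for test error, test-retest correlation and the share of children affected. It is small beside the trial's 7.3-point standard error. It may still matter within the affected group, where the excess is 1.9 to 16 points per child under the same assumptions. The primary result is not affected. This is a low-severity point, worth making because the remedy is nearly free.

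**What to change.** In Protocol 6.3.1, and in any SAP text that implements it, keep the rerun as written and add one table. For children prescribed prism and/or deliberate overminus at the 3-year visit:

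1. Score the first 3-year near Preschool Randot test with prism or overminus on its own, without requiring confirmation.
2. Cross-tabulate that status against the single-test status without prism or overminus, paired within child, separately by arm.
3. State that this contrast, not the one with the confirmed primary result, describes the effect of removing prism or overminus.

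Both scores are already taken at the 3-year exam, before control and alignment testing (Protocol 4.5 and 4.5.3), so no child is tested again. The cost is a few lines of text and one tabulation. The small downside is that the reference in this table differs from the confirmed primary definition and needs a label saying so. The test without prism or overminus always comes second, so an order effect would remain; a footnote can note it.

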**Bilateral Lateral Rectus Recession Versus Unilateral Recession-
Resect for Intermittent Exotropia**

Statistical Analysis Plan / Technical Plan

March 1, 2017

Version 1.1

1 **IXT1 Three-Year Analysis**

2
3 **1.1 Objective**

4 To compare 3-year outcomes between patients treated with bilateral lateral rectus muscle
5 recession (BLR) versus those treated with unilateral lateral rectus recession (R/R)

6
7 **1.2 Cohort of Interest**

8 197 patients with basic-type IXT with largest preoperative exodeviation between 15 and 40 PD
9 by PACT at remote distance, distance, or near (101 in BLR group, 96 in R/R group).

10
11 **1.3 Primary Outcome – Surgical Failure by 3 Years**

12 The primary outcome of surgical failure by 3 years is defined as follows:

13
14 **Failure** = ANY of the following criteria are met at masked exam occurring between 6 months
15 and 3 years after randomization:

- 16 1. **Exotropia** at distance OR near at any time during the exam (i.e., can be constant or
17 intermittent; determined by a cover/uncover test) with a magnitude of atleast 10 PD by
18 SPCT, confirmed by a retest
- 19 2. **Constant esotropia** at distance OR near (determined by at least 3 cover/uncover tests—
20 one must be before any dissociation) with a magnitude of atleast 6 PD by SPCT,
21 confirmed by a retest
- 22 3. Decrease in Preschool Randot near **stereoacuity** atleast 2 octaves (atleast 0.6 log arcsec)
23 (*see Table 3*) from the enrollment measurement, or to nil, confirmed by a retest

24
25 **Table 1: Preschool Randot Stereotest**

Baseline stereoacuity at enrollment, in arcsec	Level needed at follow up visit to meet surgical failure criteria, in arcsec
40"	200" or worse
60"	400" or worse
100"	400" or worse
200"	800" or worse
400"	Nil

26
27 Patients will also be considered a surgical failure for analysis if they undergo **reoperation** or
28 treatment with botulinum toxin at any time during the study.

29
30 **1.4 Primary Analysis**

31 The cumulative proportion of patients meeting criteria for failure by 3 years will be obtained
32 using the Kaplan-Meier method and compared between treatment groups using the Z test. This
33 will allow patients who drop out prior to 3 years to contribute to the estimation of the proportion
34 of surgical failure at 3 years. In this analysis, all patients who meet surgical failure criteria prior
35 to 3 years will be counted as failures at the first visit at which surgical failure criteria are met.

36
37 Patients who withdraw from the study or are lost to follow up without having met surgical failure
38 criteria or being reoperated will be right-censored as non-failures at the last study visit
39 completed.

40
41 **1.5 Principles to be followed in Primary Analysis**

- 42 • The primary analysis will follow the intention-to-treat principle in that all patients will be
43 analyzed according to their randomized treatment group, regardless of whether/what
44 treatment was received.
- 45 • The primary analysis will include all patients, including those who were enrolled but later
46 found to be ineligible.
- 47 • The primary analysis will also include patients who did not receive surgery, so that each
48 randomized patient can be accounted for. Inclusion of patients who did not receive
49 surgery has no impact on the K-M cumulative probability of failure because these
50 patients withdrew from the study without completing any follow up visits and are
51 therefore considered censored at time 0, before the first failure occurs and the cumulative
52 probability is calculated.
- 53 • For determining whether surgical failure criteria are met, the masked exams from all
54 protocol-specified and unspecified visits will be evaluated. *It was acknowledged that*
55 *inclusion of unspecified visits may bias the treatment group comparison if one treatment*
56 *group is seen more frequently than the other, and thus has more opportunities for the*
57 *event to be observed, and more opportunity for misclassification. It was agreed to*
58 *discuss the issue further before deciding on how to handle this in the manuscript;*
59 *however, unspecified visits are included in the abstract analyses. They have little impact*
60 *given that all patients who met failure criteria at an unspecified visit were reoperated a*
61 *short time afterward (and so would have been considered failure because of the*
62 *reoperation).*
- 63 • All masked exams that were at least partly completed will be evaluated for whether
64 surgical failure criteria are met. For example, a patient could meet surgical failure due to
65 meeting constant esotropia criteria even if stereoacuity was not able to be obtained at the
66 masked exam (e.g. stereo test was not at the location where the patient was seen).
67 Patients who did not meet surgical failure on the basis of partial masked exam data were
68 classified as not meeting failure criteria for that visit.
- 69 • Patients who appear to have met surgical failure criteria by initial testing but who did not
70 complete all required retesting for that criteria are retained in the analysis and are
71 considered not to have met surgical failure criteria.
- 72 • Patients who have not yet met surgical failure are considered to retain their non-failure
73 status throughout any subsequent consecutive missed visit(s) until this status is
74 potentially changed at a completed visit. For example, a patient who is a non-failure at a
75 completed 1 year visit, misses the 18-month and 2-year visits, and is classified as a
76 failure at a completed 30-month visit, the non-failure status from the 1 year visit is
77 maintained until the 30-month visit.

78
79 **1.6 Secondary Analysis -- Surgical Failure at 3 Year Time point**

80 The binomial proportion of patients who meet surgical failure criteria *at* the 3 year visit (as
81 opposed to *by* the 3 year visit) will be estimated for each treatment group and compared using
82 Fisher's exact test.

83
84 Patients who do not return for the 3 year visit will not be included in the analysis, including
85 patients who met surgical failure criteria at an intermediate visit or were reoperated. Patients

86 who complete the visit will be classified based on their status at 3 years, regardless of whether
87 they met surgical failure criteria at an earlier time point, unless they have been re-operated (or
88 treated with botulinum toxin), in which case they will be classified as a surgical failure.

89 The potential for bias in this treatment group comparison is recognized. Once a patient has met
90 the clinical criteria for surgical failure criteria at an interim follow up visit, the decision to
91 reoperate—and thus permanently classify the patient as a surgical failure for the analysis at 3
92 years—is at the discretion of an unmasked investigator and therefore could be related to
93 treatment group. To assist in assessing for potential bias, the association between treatment
94 group and reoperation in those meeting surgical failure criteria will be evaluated.
95

96 **1.7 Secondary Analysis -- Reoperation by 3 Years**

97 The cumulative proportion of patients undergoing reoperation or treatment with botulinum toxin
98 by 3 years will be obtained using the Kaplan-Meier method and compared between treatment
99 groups using the Z test. This outcome will include all cases of reoperation—cases where
100 reoperation was completed after surgical failure was met in addition to cases where reoperation
101 occurred without surgical failure having been met (i.e. against protocol).
102

103 The potential for bias in this treatment group comparison is recognized. Once a patient has met
104 the clinical criteria for surgical failure criteria at an interim follow up visit, the decision to
105 reoperate is at the discretion of an unmasked investigator and therefore could be related to
106 treatment group. To assist in assessing for potential bias, the association between treatment
107 group and reoperation in those meeting surgical failure criteria will be evaluated.
108

109 **1.8 Secondary Analysis – 3-Year Exotropia Control and Angle Magnitude**

110 Secondary outcomes of 3-year exotropia control (distance and near) and 3-year angle magnitude
111 by the Prism and Alternate Cover Test (distance and near) will be assessed in all patients who
112 complete the 3-year visit. All 3-year visit data will be analyzed regardless of what treatment(s) a
113 patient has received and regardless of whether the patient has undergone reoperation. These 3-
114 year control and PACT outcomes will be analyzed as continuous variables and compared
115 between treatment groups using analysis of covariance (ANOVA) models that adjust for the
116 corresponding baseline value (e.g. ANCOVA model of 3-year distance control will adjust for
117 baseline distance control).
118

- 119 **Objective #1: Define the cohort of interest**
- 120
- 121 **Objective #2: Compare the cumulative probability of surgical failure BY 3 years between**
- 122 **BLR and R/R treatment groups (primary outcome)**
- 123
- 124 **Objective #3: Compare the binomial proportion of surgical failure AT 3 years between**
- 125 **BLR and R/R treatment groups**
- 126
- 127 **Objective #4: Compare the cumulative probability reoperation by 3 years between BLR**
- 128 **and R/R treatment groups**
- 129
- 130 **Objective #5: Compare 3-year control and PACT values between BLR and R/R treatment**
- 131 **groups**
- 132
- 133
- 134

135 **Datasets Used**

136 **BASELINE** - one-record per baseline exam for all patients enrolled into in IXT1 (regardless of
137 whether randomized) N=277

138 **MASKEDEXAMS** - one-record per IXT1 masked exam (protocol-specified or unspecified) that
139 was at least partially completed IXT1 N=1344

140 **ROSTER** – one-record per randomized patient analysis dataset N=265

141 Note that the above permanent datasets include all IXT1 patients, but the analysis was limited to
142 the cohort of interest for this abstract.

143
144
145
146
147
148
149
150
151
152
153

Objective #1: Define the cohort of interest

1. 197 patients with basic-type IXT with largest preoperative exodeviation between 15 and 40 PD by PACT at remote distance, distance, or near (101 in BLR group, 96 in R/R group)

Technical plan

1. Limit the patient-level dataset ROSTER to patients where the STRATUM variable from tblStratum, the variable used to stratify the randomization, = 'Basic IXT with 15-40PD angle'

Dataset used: ROSTER

154 **Objective #2: Compare the cumulative probability of surgical failure BY 3 years between**
 155 **BLR and R/R treatment groups (primary outcome)**

- 156 1. Define the outcome
 157 2. Obtain masked exam records
 158 3. Determine whether exotropia failure criterion was met for each masked exam
 159 4. Determine whether constant esotropia failure criterion was met for each masked exam
 160 5. Determine whether stereoacuity failure was met for each masked exam
 161 5. Determine whether patient was reoperated or underwent treatment with botulinum toxin
 162 6. Calculate surgical failure at patient level and set timing variable for survival analysis (time to
 163 failure or censoring time)
 164 7. Get cumulative probability of surgical failure by 3 years for each treatment group – from K-
 165 M
 166 8. Compare cumulative probability of surgical failure by 3 years between treatment groups
 167 using a two-sided Z-test
 168 9. Calculate the treatment group difference (and 95% CI) in the cumulative probability of
 169 surgical failure by 3 years
 170

171 **Technical plan**

- 172 1. Define the outcome.

173 **Failure** = ANY of the following criteria are met at masked exam occurring between 6 months
 174 and 3 years after randomization:
 175

- 176 1. **Exotropia** at distance OR near at any time during the exam (i.e., can be constant or
 177 intermittent; determined by a cover/uncover test) with a magnitude of atleast 10 PD by
 178 SPCT, confirmed by a retest
 179 2. **Constant esotropia** at distance OR near (determined by at least 3 cover/uncover tests—one
 180 must be before any dissociation) with a magnitude of atleast 6 PD by SPCT, confirmed by a
 181 retest
 182 3. Decrease in Preschool Randot near **stereoacuity** atleast 2 octaves (atleast 0.6 log arcsec)
 183 (see Table 3) from the enrollment measurement, or to nil, confirmed by a retest
 184

185

Table 3. Preschool Randot Stereoacuity at enrollment, in arcsec	Standardized at follow up visit to meet surgical failure criteria, in arcsec
40"	200" or worse
60"	400" or worse
100"	400" or worse
200"	800" or worse
400"	Nil

186

187
 188 Patients will also be considered a surgical failure for analysis if they undergo **reoperation** or
 189 treatment with botulinum toxin at any time during the study.
 190
 191
 192

193 2. Obtain masked exam records from tblIXT1MaskedExam.

194 Include masked exams from all protocol-specified and unspecified visits.

- 195
- 196 • *It was acknowledged that inclusion of unspecified visits may bias the treatment group*
197 *comparison if one treatment group is seen more frequently than the other, and thus has*
198 *more opportunities for the event to be observed, and more opportunity for*
199 *misclassification. It was agreed to discuss the issue further before deciding on how to*
200 *handle this in the manuscript; however, unspecified visits are included in the abstract*
201 *analyses but have little impact given that all patients who met failure criteria at an*
202 *unspecified visit were reoperated a short time afterward (and so would have been*
203 *considered failure because of the reoperation).*

204 The masked exam form was a required section of data entry on the web for all follow up visits,
205 regardless of whether the masked exam was completed or was even required. Masked exams
206 records where the field maskedexamnotdone (for protocol-specified visits) or the fields
207 maskedexamnotreq or maskedexamreqnotdone (for unspecified visits) are set to 1 represent
208 masked exams that were not completed either because they could not be completed or because
209 they were not required. These records should be reviewed to confirm that they do not contain
210 data and then excluded from the analysis.

211

212

213 3. Determine whether exotropia failure criteria were met for each masked exam

- 214 • Evaluate all masked exams. *Even though only the first masked exam where failure*
215 *criteria is met is relevant to the primary outcome, save exotropia failure criteria flag*
216 *in a masked-exam-level dataset because interested in whether this criteria is met at*
217 *the 3 year visit also, and may also be interested in other visits as well.*
- 218 • Create a numeric variable for SPCT magnitude by setting '>50' equal to a nonsense
219 value of 888. *Note that no means will be calculated on this variable.*
- 220 • Exotropia failure criteria is met if the masked exam shows the patient has an exotropia
221 of 10 or greater at distance or near by SPCT, confirmed by a retest. If the worsening
222 was not confirmed by the retest or the retest was not completed, the patient was
223 considered not to have met exotropia failure criteria. Requires the following:
 - 224 ○ SPCT of ≥ 10 PD at distance or near on initial testing and retesting
 - 225 ○ Tropia type = 'Exo' at distance or near on initial testing and retesting
 - 226 ○ Note that corresponding size and type must meet above criteria for the same
227 distance for initial and retest.
- 228 • *Unlike IXT2, the exotropia does not need to be constant to meet criteria and does not*
229 *need to occur at both distance and near.*

230

231 4. Determine whether constant esotropia failure criteria were met for each masked exam

- 232 • Evaluate all masked exams. *Even though only the first masked exam where failure*
233 *criteria is met is relevant to the primary outcome, save constant esotropia failure criteria*
234 *flag in a masked-exam-level dataset because interested in whether this criteria is met at*
235 *the 3 year visit also, and may also be interested in other visits as well.*
- 236 • For each masked exam, determine whether constant esotropia failure criterion was met.
- 237 • Use SPCT variables created above.

- 238
- 239
- 240
- 241
- 242
- 243
- 244
- 245
- 246
- 247
- Constant esotropia failure criterion is met if the masked exam shows the patient has an esotropia of 6 or greater at distance *or* near (throughout exam) by SPCT, confirmed by a retest. If the worsening was not confirmed by the retest or the retest was not completed, the patient was considered not to have met constant esotropia failure criteria. Requires the following:
 - SPCT of ≥ 6 PD at distance and at near on initial testing and retesting
 - Tropia type = ‘Eso’ at distance and at near on initial testing and retesting
 - Assessment of esodeviation throughout exam = ‘Constant esotropia’ at time of initial testing and at time of retesting
- 248
5. Determine whether stereoacuity failure was met for each masked exam
- 249
